5.1 Inclusion criteria

Subjects eligible for inclusion in this study must meet **all** of the following criteria:

- Male or female patients age ≥ 28 days and < 18 years at the time of informed consent.
- Patients who have undergone alloSCT from any donor source (matched unrelated donor, sibling, haplo-identical) using bone marrow, peripheral blood stem cells, or cord blood. Recipients of myeloablative or reduced intensity conditioning are eligible.
- Patients with a clinically confirmed diagnosis of grades II-IV aGvHD within 48 hours prior to study treatment start. Patients may have either:
Treatment-naïve grades II-IV aGvHD as per [Table 8-2 \(Harris et al 2016\)](#)
OR
Steroid refractory grades II-IV aGvHD as per institutional criteria, or per physician decision in case institutional criteria are not available, and the patient is currently receiving systemic corticosteroids.
- Evident myeloid engraftment with absolute neutrophil count (ANC) $> 1000/\mu\text{l}$ and platelet count $> 20,000/\mu\text{l}$. (Use of growth factor supplementation and transfusion support is allowed.)
- Able to swallow study medication or administer the ruxolitinib oral pediatric formulation by nasogastric (NG) tube, if applicable.
- 1. Written **Study Informed** consent and/or assent from the patient, parent, or guardian at the time of Screening, i.e. at the time of treatment-naïve aGvHD or steroid refractory aGvHD diagnosis.

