6.1.1 Investigational and control drugs

Table 6-1 Dose and treatment schedule

Study treatments	Age groups	Pharmaceutical form and Route of Administration	Starting dose	Frequency and/or Regimen
Ruxolitinib (INC424)	Group 1	5-mg tablet for oral use OR oral pediatric formulation for oral or NG use *	10 mg BID (2 tablets BID) OR 10 mg BID oral pediatric formulation**	Twice per day
Ruxolitinib (INC424)	Group 2	5-mg tablet for oral use OR oral pediatric formulation for oral or NG use*	5 mg BID (1 tablet BID) OR 5 mg BID oral pediatric formulation**	Twice per day
Ruxolitinib (INC424)	Group 3	5-mg tablet for oral use OR oral pediatric formulation for oral or NG use*	4 mg/m ² BID (either tablet OR oral pediatric formulation)**	Twice per day
Ruxolitinib (INC424)	Group 4	5-mg tablet for oral use OR oral pediatric formulation for oral or NG use*	To be defined	Twice per day

*Tablet for oral use may be crushed as per instructions in the pharmacy manual (if calculated dose based on BSA is not 5 mg or 10 mg, then crushing is not permitted). Tablet cannot be broken to achieve partial doses. In this case, oral pediatric formulation should be administered (taken in liquid form). Oral pediatric formulation should be dispensed according to instructions in the pharmacy manual. Refer to the pharmacy manual for nasogastric tube administration details.

Note: Crushed tablet cannot be administered via nasogastric (NG) tube.

**BSA- based calculated doses should be administered as per instructions in the pharmacy manual.

The Investigator will instruct the patient to take the study treatment as per protocol.

All dosages prescribed and dispensed to the patient and all dose changes during the study must be recorded on the Dosage Administration Record Case Report Form (CRF).

Ruxolitinib will be administered orally or by NG tube twice per day at the assigned starting doses based on age group, given as 5-mg tablets or equivalent dose as oral pediatric formulation. Patients should remain on the same formulation throughout study participation. Any changes in formulation requires approval from the Sponsor.

Ruxolitinib (tablet or oral pediatric formulation) should be taken approximately 12 hours apart (morning and night) without regards to food. Ruxolitinib will be administered by hospital personnel in an inpatient setting, or self-administered by the patient in an outpatient setting.

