3.4.2.6 Additional systemic aGvHD therapy

New additional systemic aGvHD therapy (medications and procedures) since start of study treatment will be listed and summarized by lowest ATC class, preferred term, overall and by age group by means of frequency counts and percentages using FAS. These medications will be derived as per Appendix Section 6.4.3. Procedures are not coded by ATC class and hence they will appear under uncoded on the same table.

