6.4.3 Definition of new or additional systemic treatment for aGvHD

The data source to search for the new or additional systemic therapy is the CRF of “Prior and Concomitant Medication” (CONMED) or CRF “Prior or Concomitant non-drug therapies/procedures” and “Study treatment CNI”.

Systemic therapies are identified using the Route (if CMROUTE is Intramuscular, Intravenous, Oral, Subcutaneous, or Parenteral).

Any of the following therapies represent new or additional systemic therapy for aGvHD:

- Any CNI therapy being initiated newly as ‘treatment for aGvHD’ after the baseline (as recorded on Study treatment CNI and with indication = “treatment for aGvHD” on CONMED page). That means when a subject starts a new systemic therapy during study treatment for the indication ‘treatment for aGvHD’, or a subject received the same therapy before as prophylaxis and then changed to treatment of aGvHD as indication, this will be considered as new or additional systemic treatment.

CNI therapy given as ‘treatment for aGvHD’ that started after Day 1 will be considered as new or additional systemic treatment, even if the same therapy was given as treatment for aGvHD already before start of study treatment but the patient was not receiving such therapy on Day 1. Whereas a stop of such therapy after Day 1 and later re-start of the same therapy will not be considered as new or additional therapy.

Change of the drug within the defined group of CNIs or only change of the dose is not considered as new CNI treatment.

- Any other systemic treatments (excluding CNI and steroids) being initiated newly as ‘treatment for aGvHD’ or after the baseline and documented in CONMED (according to the same definitions as for CNI treatments above).
- Any other non-drug therapy/procedure being initiated newly as ‘treatment for aGvHD’ after the baseline (according to the same definitions as for CNI above) and documented on concomitant non-drug therapies/procedures (e.g. ECP).

Changes in the systemic corticosteroid therapy (captured on study treatment eCRF), e.g. change of the drug, the dose or any interruption and re-start, will not be taken into account for identification of new or additional systemic therapy, nor will any other corticosteroid therapy (in CONMED) be considered.

7 Reference

1. Anderson JR, Cain KC and Gelber RD (1983). Analysis of survival by tumor response. *Journal of Clinical Oncology*, 1(11), 710-719.

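### SAP 6.4.3 leaves nasogastric, gastrostomy and enteral dosing out of its systemic routes and carries a stray 'or', which mainly exposes the therapy-addition events in FFS and DOR

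*SAP*

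**What the plan says.** SAP 6.4.3 sets out how new or additional systemic treatment for aGvHD is found in the data. It names the CRF pages to search and then applies a route filter: "Systemic therapies are identified using the Route (if CMROUTE is Intramuscular, Intravenous, Oral, Subcutaneous, or Parenteral". Three bullets follow, for CNIs, other systemic drugs and non-drug procedures, under the lead-in "Any of the following therapies represent new or additional systemic therapy for aGvHD".

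The CNI bullet requires initiation for aGvHD after baseline and explains itself with "That means when a subject starts a new systemic therapy during study treatment for the indication" of treating aGvHD. The bullet for other systemic drugs instead has, after the indication, "or after the baseline and documented in CONMED (according to the same definitions as for CNI treatments above". The bullet for procedures has no such 'or'.

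SAP 3.4.2.6, on additional systemic aGvHD therapy, points to this section: "These medications will be derived as per Appendix Section 6.4.3".

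On dosing by tube, Protocol 5.1 admits a child who is "Able to swallow study medication or administer the ruxolitinib oral pediatric formulation by nasogastric (NG) tube, if applicable". Protocol 6.1.1 words the two routes as alternatives: "Ruxolitinib will be administered orally or by NG tube twice per day".

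**The concern.** The route filter is a closed list, so a program that follows it discards any record whose route is not named. Parenteral does not rescue a tube-given drug, because tube dosing is enteral. A child who starts a new immunosuppressant through a tube could therefore be left without a recorded therapy addition.

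That event matters in several places. It makes a patient a non-responder (SAP 3.5.1), removes durable response at Day 56 (SAP 3.6.1), ends the window for best overall response (BOR), ends DOR and is a component of FFS (SAP 3.7.1). Every missed event flatters the drug.

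The 'or' is a separate defect. It makes one bullet disagree with the two beside it and with the definition it cites, so two programmers could code it differently.

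**Working it through.** **1. Is tube dosing covered?** The listed routes are intramuscular, intravenous, oral, subcutaneous and parenteral. None is nasogastric, gastrostomy or enteral. The protocol distinguishes oral from NG use for ruxolitinib. Whether the concomitant-medication page does the same for other drugs cannot be seen, because its code list is not in the documents.

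**2. Which therapies could be missed?** Protocol 1.1.1 lists the second-line options. Infusions and injections pass the filter. Procedures are sought on their own CRF page, and 6.4.3 gives ECP as an example. CNIs have their own study-treatment page. That leaves enteral agents such as mycophenolate mofetil or an mTOR inhibitor, if given by tube and coded that way. The documents state no routes for these drugs, so this too is an assumption.

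**3. What else would catch a missed therapy?**

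| Endpoint | Protection outside the route filter | Exposure |
|---|---|---|
| Day 28 ORR | Response is investigator-reported, and CR and PR exclude added therapy (SAP 3.5.1). New therapy requires stopping study treatment (Protocol 6.1.5.1.1 and 9.1.1). Stopping before the Day 28 visit is complete is non-response (SAP 3.5.3). | Little |
| BOR | Investigator-assessed response with the same exclusion (SAP 3.7.2). | Limited |
| Durable ORR | Investigator-assessed CR or PR at Day 56 (SAP 3.6.1). Its list of failures does not include stopping treatment between Days 28 and 56, and assessments continue to Day 56 off treatment (Protocol 8.4.1.2). | Limited |
| DOR | A recorded progression still ends it. Response is scored against the stage at treatment start (Protocol Table 8-3), so a flare that leads to new therapy need not be recorded as progression. | Direct |
| FFS | Only a later relapse, progression of the hematologic disease or non-relapse death would register. Stopping treatment is not an event. | Direct |

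**4. What does the 'or' do?** Read alone, it splits the condition into two alternatives: started for aGvHD, or started after baseline. The same bullet then imports the CNI definitions, which require both. The lead-in and the section title also restrict every bullet to therapy for aGvHD. The bullet therefore contradicts itself, and the intended reading is the joint one.

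**5. Size.** The plan's own figure comes first. Inputs are N = 45, true ORR 80% and a two-sided 90% Clopper-Pearson interval (SAP section 4). The lower limit for r responders is the 0.05 quantile of Beta(r, 45 − r + 1).

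- r = 32: lower limit 0.580. r = 33: lower limit 0.604, upper limit 0.838. The minimum is 33, as stated.
- P(X ≥ 33 | 45, 0.80) = 0.9005, against 0.901 stated. The figure is reproduced, and correcting the wording does not change it.

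Next, the weight of one patient:

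- A proportion on 45 patients moves by 1/45 = 2.2 points.
- If one true non-responder were counted as a responder, 32 true responders would be enough: P(X ≥ 32 | 45, 0.80) = 0.948 instead of 0.901. At that boundary the reported lower limit would be 0.604 rather than 0.580. This illustrates sensitivity on Day 28 ORR, the endpoint least exposed.
- DOR uses Day 28 responders only. At the assumed 80% that is 0.80 × 45 = 36 patients, so one patient is 1/36 = 2.8 points before any censoring.
- For FFS, one missed event is 2.2 points at a landmark without censoring. If relapse or non-relapse death follows, the failure is delayed rather than lost.

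**The case against.** The strongest reply is that nothing shows a single affected patient. The tube-dosing language in the protocol concerns ruxolitinib, not how other drugs are recorded. If sites enter tube dosing as Oral, the filter works. That stands, and it makes the route point conditional. It does not remove it, because the SAP nowhere says that tube dosing is coded as Oral.

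A second reply is that the only explicit pointer to 6.4.3 is the descriptive summary in SAP 3.4.2.6. That is correct. However, the SAP offers no other definition of added systemic therapy, and FFS and DOR need a date for it. SAP Table 3-2 mentions a record of new aGvHD treatment after discontinuation, but 6.4.3 does not list that record among its sources, so it is not a written safeguard.

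A third reply is that investigator-assessed response already excludes added therapy. This stands for Day 28 ORR, BOR and durable ORR, and it is why the exposure there is rated low.

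On the other side, a reader might infer that the 'or' turns nearly every patient into a failure, because supportive anti-infectives are expected in this population. The documents do not support that. The section title, the lead-in and the cross-reference in the same bullet all limit the rule to therapy for aGvHD. A reader might also infer that procedures such as ECP drop out because they have no drug route. They do not: 6.4.3 finds them on their own CRF page.

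**Conclusion.** Both wording defects are present in SAP 6.4.3. The route omission can hide a new tube-given aGvHD drug, on the assumption that tube dosing has its own route code. The consequence falls mainly on the therapy-addition event in FFS and DOR, at about 2.2 points per patient for a 45-patient landmark and 2.8 points for 36 responders. These are weights per patient, not estimates of bias, since the number affected is unknown and may be zero. Exposure is limited for durable ORR and BOR and small for Day 28 ORR, so the documents do not support reading this as a threat to the primary endpoint. The 'or' is a drafting error that makes the bullet contradict the definition it cites. No figure stated in the plan changes.

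**What to change.** Make two edits in SAP 6.4.3 before database lock:

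- Add nasogastric, gastrostomy and enteral to the CMROUTE list. Alternatively, define systemic as every route except topical, inhaled and ophthalmic, which does not depend on listing every code.
- Delete the 'or' in the bullet on other systemic treatments, so that it requires initiation as 'treatment for aGvHD' after the baseline, in line with the CNI bullet.

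The cost is a short text change in one appendix section and the matching line of the derivation program. No new data are needed, and no edit is needed for procedures.

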5.2 Exclusion criteria

Subjects meeting any of the following criteria are not eligible for inclusion in this study.

- Has received the following systemic therapy for aGvHD:
 - a. Treatment-naïve aGvHD patients have received any prior systemic treatment of aGvHD except for a maximum 72h of prior systemic corticosteroid therapy of methylprednisolone or equivalent after the onset of acute GvHD. Patients are allowed to have received prior GvHD prophylaxis which is not counted as systemic treatment (as long as the prophylaxis was started prior to the diagnosis of aGvHD);
OR
b. SR-aGvHD patients have received two or more prior systemic treatment for aGvHD in addition to corticosteroids.
- Clinical presentation resembling de novo chronic GvHD or GvHD overlap syndrome with both acute and chronic GvHD features (as defined by [Jagasia et al 2015](#)).
 - Failed prior alloSCT within the past 6 months.
- Presence of clinically active uncontrolled infection including significant bacterial, fungal, viral or parasitic infection requiring treatment. Infections are considered controlled if appropriate therapy has been instituted and, at the time of screening, no signs of

progression are present. Progression of infection is defined as hemodynamic instability attributable to sepsis, new symptoms, worsening physical signs or radiographic findings attributable to infection. Persisting fever without other signs or symptoms will not be interpreted as progressing infection.

- Evidence of uncontrolled Hepatitis B Virus (HBV) or Hepatitis C Virus (HCV) based on assessment of treating physician.
- Evidence of clinically active tuberculosis (clinical diagnosis per local practice; skin testing is not required as not informative due to anergy).
- Known human immunodeficiency virus infection (HIV).
- Presence of relapsed primary malignancy, or who have been treated for relapse after the alloSCT was performed, or who require withdrawal of immune suppression as pre-emergent treatment of early malignancy relapse.
- Acute GvHD occurring after non-scheduled DLI administered for pre-emptive treatment of malignancy recurrence. **Note:** Patients who have received a scheduled DLI as part of their transplant procedure and not for management of malignancy relapse are eligible.
- Significant respiratory disease including patients who are on mechanical ventilation or who have resting O₂ saturation <90% by pulse-oximetry on room-air.

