- Presence of severely impaired renal function (confirmed within 72 hrs prior to study treatment start) defined by:
 - Glomerular Filtration Rate (GFR) < 30 mL/min/1.73 m² using estimated creatinine clearance calculated by updated bedside Schwartz equation or Cockcroft Gault equation OR
 - Renal dialysis requirement
 - Clinically significant or uncontrolled cardiac disease including any of the following:
 - Acute myocardial infarction within 6 months from Day 1 of study treatment administration
 - Uncontrolled hypertension
 - New York Heart Association Class III or IV congestive heart failure
 - Unstable angina within last 6 months from screening
 - Clinically significant (symptomatic) cardiac arrhythmias (e.g., sustained ventricular tachycardia, and clinically significant second or third degree AV block without a pacemaker, circulatory collapse requiring vasopressor or inotropic support, or arrhythmia requiring therapy).
 - Cholestatic disorders, or unresolved sinusoidal obstructive syndrome/veno-occlusive disease of the liver (defined as persistent bilirubin abnormalities not attributable to aGvHD and ongoing organ dysfunction).
 - History of bone disorders such as osteogenesis imperfecta, rickets, renal osteodystrophy, osteomyelitis, osteopenia, fibrous dysplasia, osteomalacia etc. prior to the underlying diagnosis which resulted in the alloSCT.
 - History of endocrine or kidney related growth retardation prior to the underlying diagnosis which resulted in the alloSCT.

- Any corticosteroid therapy for indications other than aGvHD at doses > 1 mg/kg/day methylprednisolone (or equivalent prednisone dose 1.25 mg/kg/day) within 7 days of Screening. Routine corticosteroids administered during conditioning or cell infusion is allowed.
- Current therapy with medications that interfere with coagulation or platelet function including but not limited to aspirin and related drugs, heparin, and warfarin (to minimize risk of bleeding). **Note:** Heparin or Low Molecular Weight Heparin (LMWH) is allowed if used at sub-therapeutic dose for e.g., prophylaxis of sinusoidal obstructive syndrome/veno-occlusive disease of the liver.
- History of progressive multifocal leuko-encephalopathy (PML).
 - Patients who received JAK inhibitor therapy for any indication after initiation of current alloSCT conditioning.
 - Investigational treatment within 30 days prior to treatment initiation or within 5 half-lives of the investigational product, whichever is greater.

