6.1 Study treatment

The study treatment will be administered as a 5 mg tablet or as an oral pediatric formulation (taken in liquid form) twice a day for all patients.

- Treatment-naïve aGvHD: In addition to ruxolitinib, treatment MUST include methylprednisolone (or equivalent prednisone) +/- cyclosporine or tacrolimus at standard dosing adjusted to therapeutic trough levels
- SR-aGvHD: In addition to ruxolitinib, concomitant use of corticosteroids +/- cyclosporine or tacrolimus at standard dosing adjusted to therapeutic trough levels.

In addition to study treatment, patients should receive standard alloSCT supportive care including anti-infective medications and transfusion support. Continued use of systemic corticosteroids, CNI (cyclosporine or tacrolimus), and topical corticosteroid therapy per institutional guidelines is permitted. Other systemic medications used for prophylaxis of aGvHD may be continued after Day 1 only if started prior to diagnosis of aGvHD. For SR-

aGVHD patients, cessation of other systemic treatment for aGVHD other than corticosteroids +/- CNI will be required prior to treatment initiation. Permitted concomitant therapies are described in [Section 6.2.1.1](#) and [Section 6.2.1.2](#).

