8.1 Screening

Molecular pre-screening

Not Applicable

Screening

Patients diagnosed with either aGvHD (grades II-IV) or SR-aGvHD (grades II-IV) after alloSCT will be consented to the study prior to any study procedures being performed.

Screening period will begin once the patient has signed the Study Informed Consent and will be a maximum of 28 days (Day -28 to Day -1).

Screening procedures are outlined in the visit evaluation schedule ([Table 8-1](#)) including blood samples tested as needed, and assessment of inclusion and exclusion criteria.

All study procedures should be performed within 28 days before treatment initiation on Day 1. Laboratory assessments should be performed within 72 hours of treatment initiation. Continued use of systemic corticosteroids, CNI (cyclosporine or tacrolimus), and topical corticosteroid therapy per institutional guidelines is permitted. Other systemic medications for aGvHD may be continued after Day 1 only if used for aGvHD prophylaxis prior to diagnosis of aGvHD. For SR-aGvHD patients, cessation of other systemic treatment for aGvHD other than corticosteroids +/- CNI will be required prior to treatment initiation.

A patient who has a laboratory test result(s) that does not satisfy the entrance criteria may have the test(s) repeated. These tests may be repeated as soon as the investigator believes the retest result is likely to be within the acceptable range to satisfy the entrance criteria, and can be completed within the 28 day screening period. In this case, the patient will not be required to sign another ICF, and the original patient ID number assigned by the investigator will be used.

All baseline assessments should be performed on Day 1 as per [Table 8-1](#). Laboratory assessments performed within 72 hours of Day 1 need not be repeated.

A patient is considered a screen failure in the event that the laboratory test(s) cannot be available within the screening period, or the retest(s) do not meet the entrance criteria or the patient's medical condition has changed significantly during the screening period so that the inclusion/exclusion criteria are no longer met, more details outlined on [Section 5](#).

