3.3 Patient disposition, demographics and other baseline characteristics

The Full Analysis Set (FAS) will be used for all baseline and demographic summaries and listings unless otherwise specified. Summaries will be reported by age group (defined in [Table 1-1](#)) and for all patients and listings will be reported by age group to assess baseline comparability. If more than one dose group are assigned under one age group, summaries and listings will be reported by both age group and dose group. No inferential statistics will be provided.

Basic demographic and background data

All demographic and baseline disease characteristics data will be summarized and listed by age group and for all patients. Categorical data (e.g. gender, race, ethnicity) will be summarized by frequency counts and percentages; the number and percentage of patients with missing data will be provided. Continuous data (e.g. age, weight, height, body surface area, body mass index) will be summarized by descriptive statistics (N, mean, median, standard deviation, minimum and maximum).

Diagnosis and extent of disease

Summary statistics will be tabulated for diagnosis, overall aGvHD grade at diagnosis/baseline and stem cell transplant type.

For underlying disease, the analysis will include the following: primary diagnosis classification, details of primary diagnosis, time from diagnosis of underlying disease to start of study treatment, CIBMTR risk assessment.

For transplant related disease history, the analysis will include the following: conditioning regimen type, total HCT-specific comorbidity index score, time from transplant to the start of study treatment, time from diagnosis of underlying disease to transplant, stem cell type, cytomegalovirus status, time from engraftment to start of study treatment, time from transplant to engraftment, donor information including age, gender, HLA typing method, HLA match score, source of grafts, CMV status, T-cell depleted (Y/N), total nucleated cell dose.

For aGvHD disease history, the analysis will include the following: time from diagnosis of aGvHD to start of study treatment, Overall aGvHD grade when diagnosis of aGvHD, steroid refractory aGvHD criteria met, prior aGvHD therapy (steroid only, steroid + CNI, missing), time from diagnosis of aGvHD to steroid refractory, time from steroid refractory aGvHD to start of study treatment, Overall aGvHD grade when diagnosis of SR aGvHD, and aGvHD organ involvement.

Medical history

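### SAP 6.4.3 extends its CNI exemption to all other aGvHD treatments, so a non-CNI agent wrongly still running on Day 1 escapes the additional-therapy rule

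*SAP*

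**What the plan says.** **Entry and cessation.** Protocol 5.2 excludes steroid-refractory (SR) patients only when "SR-aGvHD patients have received two or more prior systemic treatment for aGvHD in addition to corticosteroids", so one such treatment is allowed. Protocol 6.1 states that in SR patients "cessation of other systemic treatment for aGVHD other than corticosteroids +/- CNI will be required prior to treatment initiation", and 8.1 repeats it. For anything else, 8.1 adds: "Other systemic medications for aGvHD may be continued after Day 1 only if used for aGvHD prophylaxis prior to diagnosis of aGvHD". No minimum interval is set between the last dose of a second-line agent and Day 1. The only washout in 5.2 concerns investigational products: "Investigational treatment within 30 days prior to treatment initiation or within 5 half-lives of the investigational product, whichever is greater".

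**Endpoint.** Protocol Table 8-3 and section 12.4.1 deny complete or partial response when additional systemic therapy has been given for an earlier progression, mixed response or non-response. SAP 3.5.1 follows.

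**Definition.** SAP 6.4.3 says what additional therapy is. A CNI for aGvHD that the patient was not receiving on Day 1 and that starts afterwards counts, even if it had been given before. For a CNI being received on Day 1, "a stop of such therapy after Day 1 and later re-start of the same therapy will not be considered as new". The item on other systemic treatments applies "according to the same definitions as for CNI treatments above", and the item on procedures, with ECP as its example, does likewise.

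**Baseline.** SAP 3.3 summarises "prior aGvHD therapy (steroid only, steroid + CNI, missing" and offers no level for another systemic agent.

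**The concern.** The exemption makes sense for CNI, which is permitted background on Day 1; pausing and resuming it is not a new treatment. For any other systemic drug or procedure given to treat aGvHD, the protocol says that it should not be running on Day 1 at all. If it is, that is a deviation, and the SAP then treats the agent as background: continuing it, or restarting it because the disease has progressed, does not make the patient a non-responder. That contradicts Table 8-3.

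The Phase II question is the activity of ruxolitinib, estimated in a single arm with no control group to absorb such an effect. The same definition enters durable ORR, DOR and FFS. In any one patient the omission can only turn a non-response into a response, lengthen a recorded response or remove a failure event, so errors of this kind do not cancel.

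**Working it through.** **1. The plan's own figure.** Inputs from SAP section 4: N = 45, assumed true ORR 80%, two-sided 90% Clopper-Pearson interval.
- Lower limit for r responders: the 5% quantile of Beta(r, 45 − r + 1).
- The smallest r with a lower limit of at least 0.60 is 33, with interval 0.604 to 0.838.
- P(X ≥ 33 | 45, 0.80) = 0.9005, against the stated 0.901. Reproduced; no design figure is in dispute.

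**2. What 6.4.3 does in each case.** Take an SR patient whose one prior second-line agent is neither a CNI nor a steroid and was given as treatment for aGvHD.

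| Agent's course | Complies with protocol 6.1 and 8.1? | SAP 6.4.3 | Table 8-3 |
|---|---|---|---|
| Stopped before Day 1, not given again | Yes | Not counted | Response possible |
| Stopped before Day 1, restarted later for progression | Yes | Counted | Response denied |
| Running on Day 1, continued for progression, mixed response or non-response | No | Not counted | Response denied |
| Running on Day 1, stopped, restarted for progression | No | Not counted | Response denied |

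The last two rows are the conflict. Rows 2 and 4 show the oddity: the same restart makes a patient who followed the protocol a non-responder, and leaves one who did not eligible for response.

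**3. Whether another rule catches rows 3 and 4.** The Efficacy Evaluable Set (SAP 3.2) requires only assignment to the RP2D and one dose at that level. The one sensitivity analysis of Day 28 ORR (SAP 3.5.4) removes deviations in organ staging or response assessment, not in concomitant treatment. SAP 3.5.3 does make a patient who stops ruxolitinib before completing the Day 28 visit a non-responder, but that helps only if the site regards the agent as new therapy and stops ruxolitinib.

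**4. Sensitivity of the result.** The documents do not say how many patients had a non-CNI agent, or had one running on Day 1. The protocol's Amendment 3 rationale gives 45 enrolled, 71% SR: 0.71 × 45 = 31.95, about 32. Each reclassified patient moves ORR by 1/45 = 2.2 points. Starting from 36/45 (the design assumption of 80%):

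| Reclassified | Responders | ORR | 90% CI |
|---|---|---|---|
| 0 | 36 | 80.0% | 0.677 to 0.891 |
| 1 | 35 | 77.8% | 0.652 to 0.874 |
| 2 | 34 | 75.6% | 0.628 to 0.856 |
| 3 | 33 | 73.3% | 0.604 to 0.838 |
| 4 | 32 | 71.1% | 0.580 to 0.820 |

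Four reclassified responses bring the lower limit under 60%. A single one does so only when the count stands at exactly 33.

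**The case against.** The strongest reply is that the gap opens only after a deviation. In a compliant SR patient the second-line agent has stopped before Day 1, and if it comes back the same SAP paragraph counts it. The endpoint is also investigator-reported, and an investigator applying Table 8-3 should not record a response after rescue for progression. Protocol 6.2.2 and 9.1.1 require ruxolitinib to stop when new systemic therapy is needed, which leads to non-response under SAP 3.5.3. All of this stands, and it limits how many patients can be affected. It does not justify a definition that contradicts Table 8-3 in the cases where the deviation occurs.

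A reader might go further and infer that, through the restart rule, second-line effect is credited to ruxolitinib in compliant patients. Row 2 of the table shows the opposite. Residual effect of an agent stopped just before Day 1 is possible because no interval is set, but it is a separate matter from the restart rule. Patients must also have clinically confirmed grade II-IV disease within 48 hours before starting, and response is scored from the stage at that point.

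A reader might also infer that the problem is invisible in the outputs. It is not. Prior aGvHD therapy is tabulated and listed (SAP 3.4.2.1), medications continuing past the start of treatment are summarised and listed (3.4.2.7), and protocol deviations are tabulated and listed (3.3.1). What is missing is a link from these to response.

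**Conclusion.** The point holds in a limited form. Read literally, SAP 6.4.3 leaves uncounted a non-CNI, non-steroid aGvHD treatment that was wrongly running on Day 1 and is continued or restarted for progression, mixed response or non-response. That conflicts with Table 8-3 and sits badly with the cessation rule in protocol 6.1 and 8.1. The direction is favourable to ruxolitinib. The size is unknown; since a deviation is needed, a few patients at most is a reasonable judgement, but it is a judgement and not a figure from the documents.

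The 60% value is a planning marker. SAP 3.14 says that no efficacy hypothesis is tested, so crossing it would not reverse a formal decision. Nor do the documents support treating every administration after Day 1 as failure: Table 8-3 ties the loss of response to therapy given for progression, mixed response or non-response.

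**What to change.** 1. **SAP 6.4.3.** Limit both exemptions (being received on Day 1; stop and restart) to CNI. For any other non-steroid drug or procedure with aGvHD treatment as its indication, count it as additional systemic therapy if it is restarted after Day 1, or continued after Day 1 for progression, mixed response or non-response.
2. **SAP 3.5.4, sensitivity analysis.** Count all other administrations of such an agent after Day 1 (for example, a last dose without progression) as non-response here only.
3. **SAP 3.3.** Add a level to prior aGvHD therapy: steroid with or without CNI plus another systemic agent.
4. **SAP 3.5.4, descriptive split.** Show Day 28 ORR in SR patients by prior non-CNI second-line agent (yes/no), with days from its last administration to Day 1, because the protocol sets no minimum interval for such agents.

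The cost is SAP wording, one sensitivity run and one small table, using the prior and concomitant medication and procedure pages that 6.4.3 already names as its source. Enrolment is complete, and neither eligibility nor patient care changes. The downside is that ORR may come out slightly lower and that the split will rest on few patients, so it should be read as description only.
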